## 1/ Study Overview

### 1.1/ Study Synopsis

There is both a rational theoretical basis and empiric preclinical and clinical data to support using therapeutic hypothermia (TH) as a new treatment modality for ARDS. Since the reduction in metabolism by TH plus neuromuscular blockade (NMB) to block shivering reduces the requirement for pulmonary gas exchange, TH+NMB will reduce exposure of vulnerable lung parenchyma to injurious mechanical ventilation as does low tidal volume ventilation and prone positioning. However, TH also directly dampen two cell signaling pathways that contribute to lung injury, Transient Receptor Potential Cation Channel Subfamily V Member 4 (TRPV4) and p38 Mitogen-activated kinase (MAPK). The additional effects of TH on pathogenic cell signaling suggests it will confer lung protection in ARDS that is additive with current therapies. Preclinical studies demonstrate that hyperthermia worsens and hypothermia mitigates animal models of ALI through effects on leukocytes and lung endothelium and epithelium. Clinical studies of temperature management in ARDS is still at an early stage, but an older small prospective non-randomized controlled trial of TH ( $33.7\pm 0.6^{\circ}\text{C}$  for  $70\pm 15\text{h}$ ) in moribund patients with septic shock and ARDS showed improved survival in the TH group (3 of 9 vs. 0 of 10). This study preceded modern definitions and management for ARDS and mortality rates in both groups were much higher than current experience. A trial of TH ( $35^{\circ}\text{C}$ ) vs. normothermia in 31 patients with renal transplant and respiratory failure due to infection showed improved patient and renal graft survival in the TH group, but no measures of lung function were included. Our CHILL historical-controlled open-label study of TH+NMB in patients with ARDS showed TH+NMB to be safe and to improve mortality and 28-day ventilator-free days (VFDs) compared with historical controls. Although these studies were not randomized control trial (RCT), they provide strong support for our hypothesis that TH+NMB will be lung-protective in ARDS. There is additional justification for TH in COVID-19. The early autopsy studies have shown pathophysiology that looks like ARDS. Many of the cytokines released during the cytokine storm associated with severe COVID-19 pneumonia and ARDS are reduced at clinically relevant hypothermic temperatures.

We have been approved for funding by Department of Defense (DoD) to support for a 4-year multicenter RCT of TH+NMB for 48h vs. standard of care with contract to be completed June 1, 2020 and with enrollment to begin in Fall of 2020. This study was designed prior to the onset of COVID-19, which is now the most common cause of ARDS and will likely continue to be in the Fall, 2020 and perhaps beyond. Therefore, it is important to decide whether patients with COVID-19 ARDS should be enrolled in our CHILL trial. Therefore, we will conduct a 20-patient pilot safety and feasibility trial of our CHILL TH+NMB treatment vs. control in COVID-19 patients with ARDS who meet the inclusion/exclusion criteria of our DoD-funded trial. The major objective of the proposed pilot trial is to determine whether it is safe and feasible to include patients with COVID-19 ARDS in our Phase IIb CHILL RCT of TH+NMB vs. control in patients with moderate to severe ARDS.

The pilot will be conducted at the University of Maryland Medical Center. To facilitate randomization within the inclusion window, we will consent and enroll based on partial fulfillment of randomization criteria and randomize once all criteria are met. Patients will be

eligible for enrollment when they have been diagnosed with COVID-19 by PCR, and have met all Berlin criteria for moderate to severe ARDS within the 48h inclusion window except the P/F ratio  $\leq 200$  but will not be randomized until P/F ratio (measured or imputed based on SpO2) is  $\leq 200$  (while on  $\geq 8$  cm H2O PEEP and  $\geq 0.6$  FiO2). We plan to randomize a total 20 patients over 4 months to hypothermia (core temperature 34°-35°C for 48h) plus NMB or usual temperature management. The primary outcome measures will be effectiveness of cooling in achieving and maintaining the target temperature and safety measures. Secondary outcomes will include 28-day ventilator-free days (VFDs), 28-day ICU-free days, oxygen saturation index (OSI), driving pressure, Sequential Organ Failure Assessment (SOFA) score, 60-day and 90-day survival, 90-day functional assessment, cognitive assessment at ICU and hospital discharge, and biomarkers of inflammation and lung injury. Since the nature of the intervention precludes blinding, all treatment and clinical decision making related to study outcomes will be protocolized and compliance with study protocols will be monitored.

### 1.2/ Study Aims and Objectives

We will conduct the CHILL-pilot single-center RCT of TH in patients with COVID-19 and ARDS with P/F < 250 to address the following specific aims:

1. **Aim 1: Analyze the safety and feasibility and the potential lung protective effect of treating patients with COVID-19 infection and ARDS with P/F < 200 with mild TH (core temperature 34°-35°C) + NMB for 48h compared with controls receiving standard temperature management.** We expect the TH-treated group to achieve targeted temperature within 4h of randomization and to maintain TH for 48h without significant increase in serious adverse effects compared with the control arm.
2. **Analyze the potential lung protective effect of mild TH (core temperature 34°-35°C for 48h) and NMB in patients with ARDS and P/F < 200 compared with controls receiving standard temperature management.** We expect the TH-treated group to trend toward having more 28-day VFDs (primary) and 28-day ICU-FDs, and improved day-3 driving pressure and OSI than the controls.
3. **Evaluate the effects of TH on systemic inflammation and extrapulmonary organ dysfunction.** We expect the treated group to have reduced levels of proinflammatory mediators and lower Sequential Organ Failure (SOFA) scores than controls.

The proposed pilot study will determine whether we can safely include patients with COVID-19 and ARDS in our larger Phase IIb trial of TH and NMB in patients with ARDS. It will help us determine whether the 48h duration of cooling is sufficient.

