### 6/ Study Visit Schedule/Schedule of Events (see Gantt chart below)

DAYS	-2	0	1	2	3	4	7	8-27	28	ICU DC	Hospital DC	60	90
Screening data, consent, enrollment, monitor for randomization	X												
Pregnancy test (F)		F											
Randomization, baseline data, start assigned temperature management		X											
Q2h vital signs (e.g. SpO2, mean airway pressure, core temperature)		X	X	X	X	X	X						
Temperature management protocol		X	X	X	X								
ABGs		A	A	A	A	A	A						
Basic metabolic panel, CBC (times per day)		2	2	2	2	2	1						
Blood sugars (times per day)		4	4	4	4	A	A						
Research blood sample collection		X	X	X	X	X	X						
Ventilator and respiratory parameters	X	X	R	R	R	R	R						
Fluid management		X	X	X	X	X	X						
NMB status	X	X	X	X	X	X	X						
Medication review (pressors, steroids, inhaled vasodilators)		X	X	X	X	X	X						

Monitor for AEs		X	X	X	X	X	X	X	X	x	x	X	X
Calculation 28-day VFDs, ICU-FDs									X				
MOCA										X	X		
Assess Vital and functional status		X	X	X	X	X	X	X	X	X	X	X	X

X = Required (time not specified)

A = When Available

R = Measured during daily reference measurements (0600-1000). When more than one value is available, the value obtained closest to 8 a.m. will be recorded.

F = Required on females of reproductive age.

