## 8/ Study Interventions

### Temperature management:

1. Therapeutic Hypothermia Arm: The participating ICUs share an established institutional protocol for NMB and TH, which will facilitate rapid mobilization of treatment following randomization. Sedation will be adjusted to achieve a RASS -4 score and cisatracurium (Nimbex™) will be initiated and adjusted to the lowest rate that achieves nerve stimulation response of 2 twitches in train-of-four monitoring, reduction in ventilator dyssynchrony to acceptable levels, and elimination of shivering. NMB will be continued through the rewarming phase at least until core temperature reaches 35.5°C (~54h total time). Note that if the supply of Nimbex in the Clinical Pharmacy is insufficient to treat the subject, a supply of study-only Nimbex is available in the Investigational Drug Service Pharmacy.

Since the objective of CHILL-pilot is to test the effectiveness of cooling to a target temperature rather than the performance of a specific cooling device, patients in the TH arm will be cooled using one of the institution's two FDA-approved surface cooling devices, Blanketrol II cooling blankets or Arctic Sun™ cooling system. Core temperature will be reduced to 34°-35°C as quickly as possible and TH maintained for 48h. Patients will then be rewarmed to 36°C by 0.3°C/h and the cooling device removed. Post-cooling fever suppression is not part of the CHILL-pilot protocol. Cooling parameters were selected to optimize risk:benefit ratio. The criteria for early termination of hypothermia are persistent severe bradycardia (heart rate < 30 associated with mean arterial pressure <65 without vasopressor agents), uncontrolled bleeding, and intractable ventricular arrhythmias.

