### Placing the order to initiate hypothermia:

- Order sedation to RASS >-4 and Nimbex to achieve 2 twitches on train-of-four testing.
- Enter UMMC MED-CC Hypothermia Following Arrest Supplemental order set in Epic with the following modifications:
  - i. De-select: Capnography, CVP monitoring, SvO2 monitoring, NPO, Bair Hugger, Maintain MAPBP > 80 mmHg, Document Water temperature, CXR, sodium chloride 0.9% bolus, fentanyl, and vecuronium, cisatracurium.
  - ii. Under Chemistry, select Comprehensive Metabolic Panel
  - iii. Modify Hyper/Hypothermia order by changing stop date from 24h to 48 h and changing comments to: "Lower patient's temperature to **34 – 35C** as quickly as possible per protocol. Maintain **core temperature between 34 and 35C for 48 hours**. AT **48 hrs** after the initial cooling, re-warm patient no faster than **0.3** degree C per hour to **36C**." Delete "Then maintain ≤ 37C for 48 hours." (Changes from Epic order set are underlined and bolded.) These instructions have been added to the Randomization CRF.

2. Usual Temperature Management Arm: Controls will receive sedation and NMB as clinically indicated to achieve synchrony with the ventilator. During the 54h post-randomization period (corresponding with cooling and rewarming in the TH arm), acetaminophen will be given for core temperature  $>38^{\circ}\text{C}$  and surface cooling initiated for core temperature  $>38.5^{\circ}\text{C}$  and adjusted to maintain temperature  $\leq 38^{\circ}\text{C}$ . If patients are hypothermic (core temperature  $<35.5^{\circ}\text{C}$ ), surface warming will be initiated to restore core temperature to  $37^{\circ}\text{C}$ . Following the 54h treatment period, temperature management in both arms will be directed by the ICU team.

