- Enter the lowest and highest values since randomization from the EMR for systolic and diastolic blood pressure and mean arterial pressure in mm Hg in the appropriate fields on line 14. Record the lowest and highest values for CVP in cm H2O. If no CVP measurements check the “CVP not available” box. If only one measurement for any of the vital signs, enter the value in the “Lowest” CVP box and check the “Single” box.
- In the table on line 15 enter for each 6-hour period in the previous 24 hours the highest and lowest recorded core temperatures, check the box next to the location of the probe, and enter the lowest recorded SpO2 value, the corresponding FiO2, and the most concurrently measured Mean Airway Pressure. If there is only a single temperature measurement during the period, record in the “Lowest” field and check the “Single value” box. If there are no SpO2 measurements during a 2-hour period, indicate by checking the “None” Box for SpO2. If the patient was receiving supplemental oxygen by NC, calculate the FiO2 using the formula:  $F_{iO_2} = 0.21 + 0.03 \times \text{flow rate in LPM}$ .
- Indicate whether the patient received corticosteroids in the last 24 hours by checking the appropriate “Yes/No” box on line 16. If “Yes,” enter the total dose in hydrocortisone equivalents using the conversion, 1 mg prednisone or methylprednisolone = 4 mg hydrocortisone and 1 mg dexamethasone = 25 mg hydrocortisone.
- Indicate whether the patient received an inhaled vasodilator in the last 24 hours by checking the appropriate “Yes/No” box on line 17. If “Yes,” indicate which agent by checking the appropriate box and the date and time the current administration was started in the indicated field.
- Indicate if the patient received vasopressor support at any time since randomization by checking the appropriate “Yes/No” box on line 18. If “Yes,” check the box next to each of the agents that was received, the highest infusion rate (and units) received, and the total hours receiving any vasopressor support. If “No” skip to question 19.
- Indicate whether proning protocol was initiated or stopped in the prior 72 hours on line 19.
- Beginning on line 20, record the lowest and highest values for each indicated laboratory value since randomization. If there is only one value, record it in the lowest value field, and click the “Single” box. If there are no data, check the “None” box.

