Systolic BP: Lowest:  Highest:  mm Hg Single

Diastolic BP: Lowest:  Highest:  mm Hg Single

CVP: Lowest:  Highest:  cm H2O CVP not available  Single

Mean arterial pressure: Lowest:  Highest:  mm Hg Single

--	--	--	--	--	--	--	--

SITE ID PATIENT ID LETTER CODE

For each 6 hr block for the last 72 hrs record the lowest SpO2 and the FiO2 and Mean Airway Pressure measured closest to the SpO2 reading. If no SpO2 measured for block, check the "None" box.

Time Period	Date	Time	SpO 2 (pulse Ox) (%)	FiO 2 (%)	Mean airway pressure (cm H 2 O)
Day 4 after Randomization					
0600-1200					
1200-1800					
1800-2400					
Day 5 after Randomization					
00-600					
0600-1200					
1200-1800					
1800-2400					
Day 6 after Randomization					
00-600					
0600-1200					
1200-1800					
1800-2400					
Day 7 after Randomization					
00-600					

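### One fixed 48 h duration cannot show that 48 h of cooling is sufficient, and the Day 7 form omits the core temperatures needed to see late rebound

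*Protocol*

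**What the plan says.** After the three numbered aims, Protocol Section 1.2 states of the pilot: "It will help us determine whether the 48h duration of cooling is sufficient".

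Section 8 sets one cooling duration: "Core temperature will be reduced to 34°-35°C as quickly as possible and TH maintained for 48h". It continues: "Patients will then be rewarmed to 36°C by 0.3°C/h and the cooling device removed". Controls follow their own temperature rules over a matching window, "During the 54h post-randomization period (corresponding with cooling and rewarming in the TH arm"), after which the ICU team directs temperature in both arms. Section 8 also says: "Post-cooling fever suppression is not part of the CHILL-pilot protocol".

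Three places govern temperature recording on Day 7:
- The Section 6 schedule has a row "Q2h vital signs (e.g. SpO2, mean airway pressure, core temperature"), marked for days 0 to 4 and day 7.
- Section 10.7 tells staff, for line 15 of the Day 7 form, to "enter for each 6-hour period in the previous 24 hours the highest and lowest recorded core temperatures", and to mark the probe location.
- Line 15 of the printed Day 7 form reads "For each 6 hr block for the last 72 hrs record the lowest" SpO2, with the nearest FiO2 and mean airway pressure.

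The SAP describes time to target and the percentage of treatment time in range. It then fits a repeated-measures mixed model to physiological and biomarker outcomes over days 0, 1, 2, 3, 4 and 7.

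**The concern.** A trial that gives every treated patient 48 h has no contrast between durations. It can report what happens once cooling stops, but it cannot say whether a longer or shorter period would have done better. Neither document says what result would count as 48 h being enough, and no SAP analysis is aimed at that question.

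What the pilot can usefully offer the larger trial is a description of the period after rewarming: whether temperature, oxygenation and inflammatory mediators in the hypothermia arm move differently from controls. Temperature matters here because the protocol stops controlling it at that point. If the Day 7 form is used as printed, one part of that description is missing, and a statement that 48 h was enough could be made without anyone having looked at late temperature.

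**Working it through.** **Inputs.** Cooling 48 h at 34 to 35°C and rewarming to 36°C at 0.3°C/h (Section 8). A 54 h cooling-plus-rewarming window after randomisation (Section 8, control arm). Target expected within 4 h of randomisation (Section 1.2). Day 4 and Day 7 forms closing at 0800 on randomisation day +4 and +7 (collection schedule at the end of the Screening/Enrollment/Randomization form).

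**1. Reproduce the 54 h.** Duration = 48 + (36 − T)/0.3, where T is the temperature at the start of rewarming.
- T = 34: 48 + 6.7 = 54.7 h
- T = 34.5: 48 + 5.0 = 53.0 h
- T = 35: 48 + 3.3 = 51.3 h

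The plan's 54 h is consistent with this, without time to reach target. Adding 4 h and starting from 34°C gives 4 + 48 + 6.7 = 58.7 h, the latest end considered here.

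**2. Hours from randomisation to 0800 on day 4.**
- Randomised at 0001 on day 0: 4 × 24 + 8 = 104 h
- Randomised at 2400 on day 0: 104 − 24 = 80 h

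**3. Temperature recorded after rewarming.** Coverage = step 2 minus the end of rewarming.
- End at 54 h: 80 − 54 = 26 h, to 104 − 54 = 50 h
- End at 58.7 h: 80 − 58.7 = 21.3 h, to 104 − 58.7 = 45.3 h

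The daily forms up to Day 4 ask for highest and lowest temperature in 2 h blocks, so early rebound is recorded for roughly 21 to 50 h.

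**4. The gap.** From 0800 on day 4 to 0800 on day 7 is 3 × 24 = 72 h. Filling in temperature as Section 10.7 words it would recover 24 h (four 6 h blocks) and leave 48 h blank. The form's table has 3 + 4 + 4 + 1 = 12 six-hour blocks from 0600 on day 4 to 0600 on day 7. Temperature columns there would cover all but the last 2 h.

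**5. Day 7, line 15, side by side.**

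| Source | Core temperature | Probe site | Look-back |
|---|---|---|---|
| Section 6 schedule | marked for Day 7, every 2 h | not stated | not stated |
| Section 10.7 | high and low per 6 h | yes | 24 h |
| Collection schedule on the screening form | not itemised | not itemised | 24 h |
| Day 7 form, line 15 | none | none | 72 h |

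The omission is not a lost column in the PDF. The form's own instruction sentence leaves temperature out, while the equivalent sentences on the Day 03 and Day 04 forms include it. The only temperature elsewhere on the Day 7 form is in line 9: the lowest value if therapeutic hypothermia was given, which Section 10.7 defines as intentional cooling below 36°C. Fever would not appear there.

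**6. What Day 7 does collect.** SpO2, FiO2 and mean airway pressure over 72 h (the OSI inputs), plateau pressure with PEEP, and a plasma sample.

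**The case against.** The strongest reply is that little is lost. The sentence in Section 1.2 stands outside the numbered aims and says only that the pilot will help. The main purpose is safety and feasibility, and the cooling endpoints come from the earlier forms. Core temperature is measured as standard of care (Section 7.1), so missing values could probably be taken from the medical record. Only 24 h of Day 7 temperature is strictly required, because Section 10.7 and the collection schedule both look back 24 h and nothing asks for temperatures from 0800 on day 4 to 0800 on day 6. All of this stands and keeps the point modest. It does not remove the conflict on line 15, and possible retrieval is not planned retrieval.

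A reader might go further and infer any of the following. The documents do not support them.
- *Post-cooling rebound cannot be seen at all.* Early temperature rebound is recorded every 2 h, and oxygenation, airway pressures and plasma are collected at Day 7.
- *The SAP ignores the post-cooling period.* Its mixed model includes days 4 and 7. What is missing is an analysis directed at the duration question; core temperature is also not among the secondary outcomes listed in Section 1.1.
- *The background shows that late fever delays ventilator liberation.* The reanalysis in Section 1.3 reports fever in the first 3 days of ARDS and does not address study days 4 to 7.

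**Conclusion.** The point holds in a limited form. With one fixed duration, no definition of sufficiency and no directed analysis, the pilot cannot show that 48 h is sufficient, so the sentence in Section 1.2 claims a property that the design lacks. Separately, the Day 7 form omits core temperature and probe site against the protocol's own instructions, and its look-back conflicts with them. The resulting loss is temperature from 0800 on day 4 to 0800 on day 7: 72 h, of which the instructions already require 24 h. Late temperature rebound therefore cannot be seen in the trial data. Safety and cooling-performance outcomes are unaffected.

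The coverage figures assume that the forms close as the collection schedule says. The Day 03 and Day 04 forms are both headed as obtained on day 2 after randomisation, which conflicts with that schedule. If the Day 04 form really were completed on day 2, post-rewarming coverage would shrink sharply.

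**What to change.** 1. Add high and low core temperature and probe-site columns to the existing Day 7 line 15 table. Reconcile the look-back across Section 10.7, the collection schedule on the screening form, and the Day 7 form. Keeping the form's 72 h of blocks covers nearly the whole gap; 24 h is the minimum that the instructions already require. Correct the collection-day headings on the Day 03 and Day 04 forms at the same time.
2. Restate the sentence in Section 1.2: the pilot will describe, by arm, temperature, OSI and inflammatory mediators after the 54 h treatment period, and one fixed duration cannot show that 48 h is sufficient.
3. Add a descriptive line to the SAP using time points common to both arms: highest temperature per block after 54 h, and OSI and biomarkers at Days 4 and 7 against baseline or a fixed study day. Do not use change from the last on-cooling value. Controls have no such value, and the hypothermia arm rises 1 to 2°C (from 34 to 35°C up to 36°C) by protocol, which would look like rebound.

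The cost is a little more transcription from the medical record, one reworded sentence, one SAP line and a slightly less favourable claim. No clinical rule changes.

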### 1.3/ Background and Rationale

A substantial body of literature suggests that fever may worsen and hypothermia may mitigate ALI. Prior studies show that exposure to febrile-range hyperthermia (FRH) impairs endothelial barrier function, increases leukocyte transendothelial migration potential, and increases epithelial cytokine expression and apoptosis in cell culture, and worsens lung injury in animal models induced by LPS instillation, bacterial pneumonia, hyperoxia, and mechanical ventilation. In our reanalysis of core temperature and outcomes in the ICAP database, 65% of ARDS patients

had fever within the first 3 days of developing ARDS and the presence of fever reduced the likelihood of ventilator liberation within 24h by 33%. Hypothermia was lung protective compared with normothermia in animal models of ALI induced by intratracheal LPS, paraquat, hemorrhagic shock, mechanical ventilation, pneumococcal pneumonia, and air embolism. The Villar and Slutsky non-randomized concurrently controlled trial of TH in patients with septic shock and ARDS also showed a modest increase in PaO2/PAO2 ratio (0.19±0.04 vs. 0.15±0.04) in the hypothermic group. A recent small retrospective review of cardiac arrest cases showed that treatment with a standard TH protocol (core temperature 32°-34°C) tended to improve pulmonary function. Studies from our laboratory and others suggest that signaling events that cause pulmonary vascular permeability, including MAPKs and the stretch-activated ion channel, TRPV4, are suppressed by clinically relevant hypothermia, providing potential mechanisms for lung-protective effects of hypothermia. These studies provide strong support for our hypothesis that TH will benefit patients with ARDS. Because the lung pathology in COVID-19 shows many of the same features as ARDS from other causes, because of the positive results we have had in treating patients with influenza-associated ARDS, and because many of the cytokines shown to be associated with severe COVID-19 disease exhibit temperature-dependent expression, we expect that our TH+NMB protocol will be safe, feasible, and beneficial in patients with COVID-19 ARDS.

